### 12.3.3 Assessment of Potential Risks and Benefits

Risks to participants have been minimized in the study and involve no more than that expected from standard of care monitoring of MDS, which includes regular peripheral blood draws and bone marrow evaluations. The potential disease modifying/therapeutic benefit of KPT-8602 as an investigative agent outweighs the risks discussed, which are otherwise mostly standard procedures for participants with MDS.

## 12.4 CONSENT AND ASSENT PROCESS AND DOCUMENTATION

The informed consent document will be provided as a physical or electronic document to the participant for review prior to consenting. A designated study investigator will carefully explain the procedures and tests involved in this study, and the associated risks, discomforts and benefits. In order to minimize potential coercion, as much time as is needed to review the document will be given, including an opportunity to discuss it with friends, family members and/or other advisors, and to ask questions of any designated study investigator. A signed informed consent document will be obtained prior to entry onto the study.

The initial consent process as well as re-consent, when required, may take place in person or remotely (e.g., via telephone or other NIH approved remote platforms used in compliance with policy, including HRPP Policy 303) per discretion of the designated study investigator and with the agreement of the participant/consent designee(s). Whether in person or remote, the privacy of the subject will be maintained. Consenting investigators (and participant/consent designee, when in person) will be located in a private area (e.g., clinic consult room). When consent is conducted

remotely, the participant/consent designee will be informed of the private nature of the discussion and will be encouraged to relocate to a more private setting if needed.

Consent will be documented with required signatures on the physical document (which includes the printout of an electronic document sent to participant) or on the electronic document. Signatures on electronic documents are described below.

Manual (non-electronic) signature on electronic document:

When a manual signature on an electronic document is used for the documentation of consent at the NIH Clinical Center, this study will the following to obtain the required signatures:

- Adobe platform (which is not 21 CFR Part 11 compliant); or,
- iMedConsent platform (which is 21 CFR Part 11 compliant)

During the consent process, participants and investigators will view individual copies of the approved consent document on screens at their respective locations (if remote consent); the same screen may be used when in the same location, but is not required.

Both the investigator and the participant will sign the document using a finger, stylus or mouse.

Note: Refer to the CCR SOP PM-2, Obtaining and Documenting the Informed Consent Process for additional information (e.g., verification of participant identity when obtaining consent remotely) found at:

<https://ccrod.cancer.gov/confluence/pages/viewpage.action?pageId=73203825>.

## **13 REGULATORY AND OPERATIONAL CONSIDERATIONS**

### **13.1 STUDY DISCONTINUATION AND CLOSURE**

This study may be temporarily suspended or prematurely terminated if there is sufficient reasonable cause. Written notification, documenting the reason for study suspension or termination, will be provided by the suspending or terminating party to study participants, investigators, funding agency, the Investigational New Drug (IND) or Investigational Device Exemption (IDE) sponsor and regulatory authorities. If the study is prematurely terminated or suspended, the Principal Investigator (PI) will promptly inform study participants, the Institutional Review Board (IRB), and sponsor and will provide the reason(s) for the termination or suspension. Study participants will be contacted, as applicable, and be informed of changes to study visit schedule.

Circumstances that may warrant termination or suspension include, but are not limited to:

- Determination of unexpected, significant, or unacceptable risk to participants
- Demonstration of efficacy that would warrant stopping
- Insufficient compliance to protocol requirements
- Data that are not sufficiently complete and/or evaluable
- Determination that the primary endpoint has been met
- Determination of futility

Study may resume once concerns about safety, protocol compliance, and data quality are addressed, and satisfy the sponsor, IRB and as applicable, Food and Drug Administration (FDA).

### **13.2 QUALITY ASSURANCE AND QUALITY CONTROL**

The clinical site will perform internal quality management of study conduct, data and biological specimen collection, documentation and completion. An individualized quality management plan will be developed to describe a site's quality management.

Quality control (QC) procedures will be implemented beginning with the data entry system and data QC checks that will be run on the database will be generated. Any missing data or data anomalies will be communicated to the site(s) for clarification/resolution.

Following written Standard Operating Procedures (SOPs), the monitors will verify that the clinical trial is conducted and data are generated and biological specimens are collected, documented (recorded), and reported in compliance with the protocol, International Council on Harmonisation Good Clinical Practice (ICH GCP), and applicable regulatory requirements (e.g., Good Laboratory Practices (GLP), Good Manufacturing Practices (GMP)).

The investigational site will provide direct access to all trial related sites, source data/documents, and reports for the purpose of monitoring and auditing by the sponsor, and inspection by local and regulatory authorities.

### **13.3 CONFLICT OF INTEREST POLICY**

The independence of this study from any actual or perceived influence, such as by the pharmaceutical industry, is critical. Therefore, any actual conflict of interest of persons who have a role in the design, conduct, analysis, publication, or any aspect of this trial will be disclosed and managed. Furthermore, persons who have a perceived conflict of interest will be required to have such conflicts managed in a way that is appropriate to their participation in the design and conduct of this trial. The study leadership in conjunction with the National Cancer Institute has established policies and procedures for all study group members to disclose all conflicts of interest and will establish a mechanism for the management of all reported dualities of interest.

### **13.4 CONFIDENTIALITY AND PRIVACY**

Participant confidentiality and privacy is strictly held in trust by the participating investigators, their staff, and the sponsor(s). This confidentiality is extended to cover testing of biological samples and genetic tests in addition to the clinical information relating to participants. Therefore, the study protocol, documentation, data, and all other information generated will be held in strict confidence. No information concerning the study or the data will be released to any unauthorized third party without prior written approval of the sponsor.

All research activities will be conducted in as private a setting as possible.

The study monitor, other authorized representatives of the sponsor, representatives of the Institutional Review Board (IRB), and/or regulatory agencies may inspect all documents and records required to be maintained by the investigator, including but not limited to, medical records (office, clinic, or hospital) and pharmacy records for the participants in this study. The clinical study site will permit access to such records.

The study participant's contact information will be securely stored at the/each clinical site for internal use during the study. At the end of the study, all records will continue to be kept in a secure

location for as long a period as dictated by the reviewing IRB, Institutional policies, or sponsor requirements.

Study participant research data, which is for purposes of statistical analysis and scientific reporting, will be transmitted to and stored at the NCI CCR. This will not include the participant's contact or identifying information. Rather, individual participants and their research data will be identified by a unique study identification number. The study data entry and study management systems used by the clinical site(s) and by NCI CCR research staff will be secured and password protected. At the end of the study, all study databases will be archived at the NCI CCR.

To further protect the privacy of study participants, a Certificate of Confidentiality has been issued by the National Institutes of Health (NIH). This certificate protects identifiable research information from forced disclosure. It allows the investigator and others who have access to research records to refuse to disclose identifying information on research participation in any civil, criminal, administrative, legislative, or other proceeding, whether at the federal, state, or local level. By protecting researchers and institutions from being compelled to disclose information that would identify research participants, Certificates of Confidentiality help achieve the research objectives and promote participation in studies by helping assure confidentiality and privacy to participants.

## 14 PHARMACEUTICAL AND INVESTIGATIONAL DEVICE INFORMATION

### 14.1 KPT-8602 (IND # 163958)

#### 14.1.1 Description

[figure not shown]
	Current formulations
Dosage form	Tablet
Route of administration	Oral
Strength(s)a	5 mg, 10 mg
Manufacturing process	Roller compaction dry granulation: API and inactive excipients are blended before roller compaction to make granules. Granules are further blended with additional excipients and subsequently compressed, then film coated.
Componentsb	eltanexor (KPT-8602) ~6.25% by weight for 5 mg and 10 mg microcrystalline cellulose mannitol providone croscarmellose sodium colloidal silicon dioxide sodium lauryl sulfate magnesium stearate
Coating	Opadry 200 Clear (sub-coat) and Opadry II Orange (top-coat)
Color	Orange to peach
Packaging	HDPE bottles with desiccant
Shipping	2-25°C
Storage	Store at or below 25°C. Do not freeze.

aTablet strengths are distinguished by tablet size and debossing (5 mg tablets are scored, 10 mg tablets have no debossing)

bThese tablet components/excipients are common to oral pharmaceuticals and/or compendial.

**Chemical structure:**

5-Pyrimidineacetamide,  $\alpha$ -[[3-[3,5-bis(trifluoromethyl)phenyl]-1*H*-1,2,4-triazol-1-yl]methylene]-, ( $\alpha$ *E*)-(*E*)-3-(3-(3,5-bis(trifluoromethyl)phenyl)-1*H*-1,2,4-triazol-1-yl)-2-(pyrimidin-5-yl)acrylamide

- **Molecular weight:** 428.30 g/mol
- **Mechanism of action:** selective inhibitor of nuclear export (SINE)

#### 14.1.2 Source/Acquisition and Accountability

KPT-8602 (eltanexor) is manufactured and supplied for the trial by Karyopharm Therapeutics, Inc.

KPT-8602 will be provided to the clinical trial site by the manufacturer. The investigator or designee (e.g., pharmacist) will maintain an ongoing inventory of the investigational product supply according to standard site procedures. The investigational product will be dispensed at the direction of an investigator for administration to a study participant enrolled on the clinical trial. Disposal of expired or unused product will be returned to the manufacturer or disposed of according to standard site procedures based on agreement between the manufacturer and the site

#### 14.1.3 Toxicity

The key preclinical safety findings in rats and monkeys are as follows:

- In general, the major effects across the toxicology studies was non-adverse, reversible weight loss, some of which also observed for other SINE compounds (selinexor, verdinexor, etc). The effects on body weight were typically associated with lower food consumption, were fully reversible, and considered non-adverse.
- Eltanexor-related effects in male rat reproductive tissues were dependent on dosing frequency and duration, consistent with other SINE compounds. In the 4-week rat GLP study (QD $\times$ 5/week), non-adverse microscopic findings were reported for the testes. In rats given 20 doses at  $\geq$ 4 mg/kg (24 mg/m^2), minimal-mild germ cell degeneration in the testes was accompanied by minimal-mild cellular debris in the epididymis; these findings were non-adverse and fully reversible after a 28-day recovery period. In monkeys, there were no adverse effects observed.
- In the GLP, 4-week study in monkeys (QD $\times$ 5/week), serum chemistry measures indicated significantly higher serum amylase and lipase. These correlated to microscopic findings in the pancreas including acinar atrophy, acinar hyperplasia (males), individual cell

degeneration/necrosis, interstitial fibrosis, and ductal hypertrophy/hyperplasia (males). Following a 28-day recovery period, effects on the pancreas were fully reversible, except for minimal pancreatic acinar atrophy, interstitial fibrosis, ductal hypertrophy/hyperplasia, and minimally decreased zymogen granules. Based on these results, eltanexor is not considered to pose a risk for pancreatitis.

- Eltanexor was not genotoxic in a GLP *in vitro* bacterial reverse mutation (Ames assay).

The safety, tolerability, and preliminary efficacy of eltanexor in humans is currently under investigation in Study KCP-8602-801 (Study 801) which is an ongoing first-in-human, open-label dose-escalation study in patients with relapsed/refractory multiple myeloma (R/R MM) followed by a dose-expansion phase in patients with select advanced malignancies. As of 18 November 2021, a total of 124 patients have received eltanexor in Study 801, of which 119 patients (39 patients with R/R MM, 30 patients with mCRPC, and 20 patients with HR-MDS) have safety data available. In the entire safety population, the most frequently occurring TEAEs of any grade were nausea (63%), fatigue (63%), diarrhea (58%), decreased appetite (49%), thrombocytopenia (49%), weight decreased (48%), anemia (45%), vomiting (45%). The most frequently occurring  $\geq$  Grade 3 TEAEs were thrombocytopenia (31%), anemia (29%), and neutropenia (25%). However, no clinically significant cumulative toxicities were identified, major organ dysfunction was not observed, and no grade 5 TRAEs were reported. Adverse events leading to discontinuation of eltanexor that occurred in  $\geq$  3 patients were fatigue (6.7%), nausea (4.2%), sepsis (3.4%), as well as vomiting, acute kidney injury, decreased appetite, and weight decreased (2.5% each). See the Eltanexor Investigator's Brochure (IB) for more information.

#### 14.1.4 Formulation and preparation

Eltanexor is an immediate-release tablet for oral administration. Initial supplies came in 2 strengths: 5 mg and 20 mg of the active pharmaceutical ingredient per tablet. The 20 mg tablet is no longer being used. Current supplies for the clinic are 5 mg and 10 mg tablets, where the 10- mg tablet is weight proportional (2 $\times$ ) with respect to the 5-mg tablet. All inactive ingredients used in the tablets are either compendia or generally recognized as safe. Tablets are film coated for ease of handling. Detailed information related to the manufacturing, components/excipients, packaging, and storage of the drug formulations is provided in the Eltanexor IB.

#### 14.1.5 Stability and Storage

Eltanexor tablets are packaged in white high-density polyethylene bottles with induction seals with polypropylene caps. The eltanexor-containing bottles should be stored at/or below 25°C but not frozen.

#### 14.1.6 Administration Procedures

See Section [3.2.1](#).

#### 14.1.7 Incompatibilities

The primary metabolism of eltanexor based on nonclinical studies *in vitro* and *in vivo* appears to involve inactivation by GSH conjugation. This process can be mediated in the absence of proteins, indicating that it is thermodynamically favorable. *In vitro* studies using human liver microsomes indicate that eltanexor undergoes minimal CYP450 mediated metabolism. There was also minimal to no induction of CYP450 activity observed for CYP1A2, CYP2B6, or CYP3A4.

Therefore, the risk of drug-drug interactions with eltanexor is low; however, administration of eltanexor with drugs that undergo substantial GSH conjugation should be minimized. These drugs include acetaminophen (paracetamol). In the event that GSH depletion is believed to be contributing to patients' symptoms, signs or laboratory findings, replenishment with SAM (S-adenosyl-L-methionine) oral (e.g., 400 mg) or N-acetylcysteine (e.g., up to 140 mg/kg loading dose followed by 70 mg/kg Q4 hours) until symptoms resolve. It should be noted that no studies of eltanexor in combination with acetaminophen have been performed to date and that these recommendations are empirical.

Eltanexor is also a substrate for BCRP and a marginal substrate of P-gp, therefore concomitant administration of inhibitors of BCRP and P-gp should be avoided. (Examples can be found at the following link: <https://www.fda.gov/drugs/drug-interactions-labeling/drug-development-and-drug-interactions-table-substrates-inhibitors-and-inducers#table5-2>)

The effect of concomitant administration of gastric acid reducing agents on eltanexor PK cannot be ruled out at this time, therefore concomitant administration of acid-reducing agents, e.g. proton pump inhibitors or H2-receptor antagonists, with eltanexor during the dose finding portion of the study will be avoided.

There are no other known drug interactions.

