## 2.1.2 Exclusion Criteria

2.1.2.1 Participants with platelet transfusion-refractory thrombocytopenia, with inability to keep platelet threshold above 10K/mcL with transfusions or those with ongoing or uncontrolled hemorrhagic complications.

2.1.2.2 Participants with clinically significant neutropenia, defined as ANC <100 cells/mcL with frequent hospitalizations for infection (average > 1 hospitalization per month in the past 6 months).

2.1.2.3 Participants on treatment with a myeloid growth factor (e.g., G-CSF) within 14 days prior to initiation of study treatment.

2.1.2.4 History of allergic reactions attributed to compounds of similar chemical or biologic composition to HMAs or other agents used in study.

2.1.2.5 Uncontrolled intercurrent illness evaluated by history, physical exam, and chemistries or situations that would limit compliance with study requirements, interpretation of results or that could increase risk to the participant

2.1.2.6 Participants with the following cardiac conditions: symptomatic congestive heart failure, unstable angina pectoris, or uncontrolled cardiac arrhythmia as assessed by electrocardiogram (ECG).

- 2.1.2.7 Pregnancy (confirmed with  $\beta$ -HCG serum or urine pregnancy test performed in individuals of childbearing potential at screening)
- 2.1.2.8 Presence of any other malignancy (except basal and squamous cell carcinoma of the skin, or stable chronic cancers on hormone or targeted therapy) for which participant received systemic anticancer treatment (except maintenance therapy) within 24 months prior to treatment.
- 2.1.2.9 Participants with active/uncontrolled Hepatitis B
- 2.1.2.10 Participants with active/uncontrolled Hepatitis C
- 2.1.2.11 Participants with active/uncontrolled HIV infection or AIDS.
- 2.1.2.12 Participants currently taking contraindicated medications for HIV, Hepatitis B, or Hepatitis C disease control ([Appendix L](#))

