### **3.3 DOSE MODIFICATIONS**

Participants may continue study treatment if toxicity can be managed by interruption of the dose of study treatment or dose reductions as explained below. The following outlines dose modifications for study-drug related toxicities.

If toxicity is considered to be due solely to one of the study drugs as defined below, the participant may be taken off this drug and after consulting with a Sponsor may continue treatment with the other drug only if the participant is deriving benefit from treatment in the form of stabilization of disease or response.

When, at the beginning of a treatment cycle, treatment delay related to one drug is indicated, treatment with the other drug will be continued. For the purpose of restaging, cycle number will continue to be defined on the basis of a time of 28 days (+/- 7 days), i.e., cycle number will not change due to one drug being held.

Overlapping toxicities may be attributed solely to KPT-8602 if a participant who was already on Inqovi prior to starting on study treatment develops the toxicity upon addition of KPT-8602. In addition, overlapping toxicities may be attributed solely to one of the drugs if dose modification or delay of one drug (while the other is continued at the same dose) results in resolution of the toxicity.

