### 3.3.2.2 Toxicity Guidelines

In addition, the tables below show general supportive care and dose modification guidelines for toxicities noted at any point during study treatment (other than the scenarios described above). Dose levels of KPT-8602 and Inqovi for the purposes of toxicity management are as noted in Section 3.3.1.

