### 3.3.2.2.1 Hematologic toxicities

Toxicity	Recommended Action*
Thrombocytopenia	
Grade 2 (PLT $\leq$ 75,000/mcL)	
 
Maintain dose of KPT-8602 and Inqovi.
 
Consider dose reduction of any anti-platelet agents.
 
Start PPI.
 

Grade 3 or 4 thrombocytopenia (PLT $\leq$ 50,000/mcL) without bleeding	
 
In cases where there is still significant disease involvement in the bone marrow:             
 
The treating physician, in consultation with the PI, may continue KPT-8602 and Inqovi at the same dose level
 
 
 
Otherwise, the following guidelines should be followed:             
 
Hold KPT-8602 and Inqovi until improves to <math>\leq</math> Grade 2 or baseline.                     
 
If improves to <math>\leq</math> Grade 2 or baseline within 72 hours:                             
 
Resume KPT-8602 and Inqovi at the same dose
 
 
 
If does not improve to <math>\leq</math> Grade 2 or baseline within 72 hours:                             
 
Hold KPT-8602 and Inqovi for the remainder of the current cycle.
 
Reduce KPT-8602 by one dose level with the next cycle
 
Resume Inqovi at the same dose for the next cycle (first occurrence) or reduce Inqovi by one dose level for the next cycle (second or later occurrences)
 
Note: Toxicity must resolve to <math>\leq</math> Grade 2 or baseline before drugs can be resumed
 
 
 
 
 
In addition, the following steps should be taken for all cases:                     
 
Consider initiating a platelet growth factor per institutional guidelines.
 
Monitor platelet counts at least twice weekly and closely monitor for any bleeding signs/symptoms.
 
Transfuse as per institutional guidelines.
 
Consider dose reduction of any anti-platelet agents.
 
Start PPI.
 
 
 
 
 

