#### 4.1.2 Hematologic Support

- Due to the hematologic abnormalities associated with MDS, management of hematologic toxicity in MDS participants will be at the discretion of the PI/treating investigator.
- Transfusions of red blood cells and platelets will be allowed per the appropriate participant-specific hematologic parameters.
- G-CSF may be administered for participants with ANC < 500/mcL per the discretion of the treating physician.
- Thrombopoietin agonists may be administered for participants with PLT < 50 x 10^9/L per the discretion of the treating physician.

- Participants receiving a stable dose of erythropoiesis-stimulating agent (ESA) for at least 1 month at the time of study entry may continue to receive ESA, but changes in dosing of ESA or new start of ESA within <30 days are not permitted.

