### 4.2 DRUG INTERACTIONS

The risk of drug-drug interactions with KPT-8602 is low. However, administration of eltanexor with drugs that undergo substantial GSH conjugation (e.g., acetaminophen) should be minimized. See Section [14.1.7](#).

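### Section 14.1.7 avoids acid reducers with eltanexor during dose finding, but the thrombocytopenia table recommends a PPI while KPT-8602 continues and makes no Phase I exception

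*Combined protocol and SAP*

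**What the plan says.** **The restriction.** Section 14.1.7 names PPIs and H2-receptor antagonists as examples of acid-reducing agents whose use "with eltanexor during the dose finding portion of the study will be avoided". The reason given is that an effect on eltanexor PK has not been excluded.

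**The toxicity table.** Section 3.3.2.2 introduces its tables as covering supportive care and "dose modification guidelines for toxicities noted at any point during study treatment", without a phase limit. In the thrombocytopenia part of 3.3.2.2.1:

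- Grade 2: "Maintain dose of KPT-8602 and Inqovi", and start a PPI, both in the same cell.
- Grade 3-4 without bleeding: with significant marrow disease, the physician, in consultation with the PI, "may continue KPT-8602 and Inqovi at the same dose level". Starting a PPI is among the steps listed for all cases.
- Grade 3-4 with bleeding: start a PPI, and hold both drugs for the rest of the cycle.

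**Related text.** The action column is headed as recommended. Section 4.1.2 says that "management of hematologic toxicity in MDS participants will be at the discretion of the PI/treating investigator". Section 4.2 opens with "The risk of drug-drug interactions with KPT-8602 is low", warns about acetaminophen and similar drugs, and refers the reader to 14.1.7. Neither section says how the PPI step is to be handled in Phase I, and nor do Sections 3.1.1 and 4.3.

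**The endpoint concerned.** KPT-8602 PK is the Phase I secondary objective (Sections 1.1.2 and 10.1). Section 10.4.3 summarises AUC, half-life and steady-state concentration descriptively for each dose level.

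**The concern.** An investigator who follows the Grade 2 row in Phase I gives eltanexor and a PPI together, which is the combination 14.1.7 sets out to avoid. Someone working from the toxicity table meets no reminder of the restriction there.

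What is at stake is how cleanly the Phase I PK summary can be read. Dose levels hold 3-6 participants (Section 3.1.2), so a few profiles taken on a PPI could shift a level's descriptive statistics, and Section 10.4.3 has no step to identify them. Phase II repeats the PK schedule at the RP2D (Section 5.2.1.2), but 14.1.7 confines the restriction to dose finding. Phase I is therefore the only part of the trial that the protocol intends to keep free of acid reducers.

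The trigger is not rare. Section 1.2.3.2 reports thrombocytopenia in 30% of the eltanexor MDS cohort (n = 20). Section 14.2.2 lists decreased platelets among the Grade 3 or 4 laboratory abnormalities seen in at least 50% of patients on Inqovi. These figures do not estimate how many Phase I participants would receive a PPI.

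**Working it through.** The plan gives no figure to reproduce. The check has two parts.

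**1. Do the rules collide?**

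| Situation in Phase I | KPT-8602 | PPI by the table | Consistent with 14.1.7? |
|---|---|---|---|
| Grade 2 | maintained | start | No |
| Grade 3-4, no bleeding, significant marrow disease | may continue | start | No, if continued |
| Grade 3-4, no bleeding, otherwise | held until recovery | start | Only while held; the table does not say to stop the PPI when KPT-8602 resumes |
| Grade 3-4 with bleeding | held for the rest of the cycle | start | Only while held, as above |

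The first two rows give direct co-administration.

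**2. How many PK samples could be affected in one participant?**

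Inputs:

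- Sampling times (Section 5.1). The 24 h entry printed twice for Day 8 at levels -2 and 1 is counted once.
- First KPT-8602 dose on Day 8 (Section 3.1.2).
- Cycle 1 blood counts on Days 1, 8, 15 and 22 (Section 3.5.1).
- The C2D15 and C3D15 troughs are left out, because Section 10.1 defines the endpoint from cycle 1.

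Cycle 1 samples:

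- Levels 1 and -2: Day 8 profile (pre-dose, 1, 2, 3, 4, 8, 24 h) = 7. Day 12 profile (pre-dose, 2, 3, 8, 24, 48 h) = 6. Total 7 + 6 = 13.
- Levels 2 and -1: Day 8 profile = 7. Day 21 profile (pre-dose, 1, 3, 4, 8, 24, 48 h) = 7. Total 7 + 7 = 14.

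*PPI started from the Day 15 count* (the first scheduled count after KPT-8602 begins on Day 8):

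- Levels 1 and -2: the last sample is on Day 14, so 0 of 13 are exposed.
- Levels 2 and -1: the Day 21-23 profile follows, so up to 7 of 14 (7/14 = 50%) are exposed.

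*PPI started by Day 8 for Inqovi-related thrombocytopenia:*

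- The Day 8 pre-dose sample is drawn before any eltanexor, so a PPI cannot alter it.
- Levels 1 and -2: at most 13 - 1 = 12 of 13.
- Levels 2 and -1: at most 14 - 1 = 13 of 14.

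An unscheduled count between Day 8 and Day 15 would give a result between these two cases.

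**The case against.** **The texts can be read together.** The table offers general recommendations for both phases, 14.1.7 is a specific rule for one drug class in one phase, and 4.2 points to it. Section 4.1.2 leaves hematologic management to the investigator, who may withhold the PPI. The table already gives way to Phase I text elsewhere, since Section 3.1.1 bars dose reductions and interruptions in the DLT window although the table recommends them. All of this stands, and it is why the point is minor. It does not remove the contradiction. Discretion lets an investigator avoid the combination, but the two instructions still disagree, and 3.1.1 says nothing about PPIs.

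**The endpoint is descriptive and there are safeguards.** Concomitant medications are already recorded (Section 3.4.2) and PK is sampled again in Phase II. This also stands and limits the stakes.

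Three stronger readings are tempting, and the documents do not support them:

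- *Every PK sample could be exposed.* The Day 8 pre-dose sample cannot be affected, and the sparse troughs lie outside the endpoint as Section 10.1 defines it. At levels 1 and -2 those troughs also fall about 72 h after the Day 12 dose. With the 4-6 h half-life in Section 1.2.3.3, that is 72/6 = 12 to 72/4 = 18 half-lives, so they hold almost no drug.
- *Low platelets at entry would start a PPI on Day 1.* Section 2.1.2 excludes only severe cases, such as "inability to keep platelet threshold above 10K/mcL with transfusions" in platelet-refractory participants, so low counts at entry are possible. But Section 3.3 says: "The following outlines dose modifications for study-drug related toxicities". Thrombocytopenia present before any study dose does not clearly qualify. Inqovi-related thrombocytopenia on the Day 8 count fits the text better.
- *DLTs or the RP2D could be biased.* Section 14.1.7 says only that a PK effect cannot be excluded. It gives neither size nor direction, and Section 1.2.3.3 sets the RP2D from the MTD.

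**Conclusion.** The contradiction is real and minor. In Phase I, following the Grade 2 row produces the combination that 14.1.7 says to avoid. The same holds for the Grade 3-4 non-bleeding row when KPT-8602 continues. The consequence is possible confounding of a descriptive secondary endpoint and goes no further.

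The sample counts are ceilings for one participant, not estimates of frequency. They assume that the PPI is started on the day of the triggering count, that counts are taken as scheduled, and that only cycle 1 samples matter. How many participants would be affected, and whether a PPI raises or lowers eltanexor exposure, cannot be determined from the documents. The point is still worth correcting because the protocol has already chosen to protect Phase I PK, and the table works against that choice.

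**What to change.** - **Section 3.3.2.2.1:** state that during Phase I the PPI step does not apply routinely while KPT-8602 is being given, in line with 14.1.7, except for bleeding or another clinical need judged by the investigator.
- **Section 14.1.7:** add the same exception, so that the two sections agree.
- **PK summary (Section 10.4.3):** use the existing concomitant-medication record to flag Phase I profiles taken on an acid reducer.
- **Section 4.2:** repeating the rule is optional, because it already refers to 14.1.7.

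The cost is a few lines of amendment wording and a flag in one descriptive summary, with no new data collection. With 3-6 participants per level, the flag helps interpretation but cannot support a formal comparison. The clinical downside is slightly less routine gastric protection for non-bleeding Phase I participants. Relaxing 14.1.7 instead would also remove the clash, but it would give up the PK safeguard.
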